1. The primary endpoint of this study is whether mpMR parameters measured after 2 months of neoadjuvant ADT therapy (TP1) correlate with nadir PSA post 8-weeks of ADT. In addition, we will determine whether mpMR parameters in areas of tumor (T) in those who fail neoadjuvant ADT (defined as PSA end ADT values $>.3$ ng/ml) are different to those who respond to ADT (defined as PSA end ADT $\leq.3$ ng/ml).
2. A secondary endpoint of this study is whether mpMR parameters measured after 6 weeks of EBRT (TP2) and 8 weeks after completion of EBRT (TP3) correlate with end PSA (defined as PSA level immediately after EBRT treatment). In addition, we will determine whether mpMR parameters in areas of T in those likely to fail combined ADT/EBRT (defined as PSA end values $>.5$ ng/ml) are different to those of responders (PSA end values $\leq.5$ ng/ml).

IV Subject selection

1. Inclusion criteria:
 - a. Adult males with unfavorable intermediate- to high-risk localized disease identified as one of the following three categories for unfavorable intermediatehigh risk factors, but must have visible disease on baseline MRI.
 - i. Clinical or radiographic T2b-T4 primary tumor
 - ii. Gleason score 7-10 in any core
 - iii. PSA ≥ 10 prior to initiation of therapy
 - b. Patients are deemed suitable for therapy with ADT and EBRT.
 - c. Subjects must be able to provide informed written consent prior to study entry.
2. Exclusion criteria:
 - a. The standard exclusion criteria for MRI exams will apply which include patients with pacemakers, non-compatible intra-cranial vascular clips, inner ear implants, and severe claustrophobia.
 - b. Patients who because of age, general medical or psychiatric condition, or physiologic status unrelated to the presence of prostate cancer are unlikely to be candidates for repeat MRIs, or cannot give valid informed consent.
 - c. Patients unwilling or unable to undergo the ecoli placement or multiparametric MRI exam.
 - d. Patients with a history of allergic reaction to latex or Gadolinium containing intravenous contrast agents.

- e. Individuals with renal disease or other contraindications to gadolinium will be excluded. The BWH standard MRI contrast screening criteria will be used to establish renal status.
- f. Patients who have had prior prostatectomy or prior androgen therapy.

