We estimate that 25% of men with grade T2c or greater cancer will have end PSA greater than 0.5, and will fail therapy. Barrett et al. reported a change in ADC between three months of ADT and a preADT baseline in tumor of -0.028 with a SD of 0.227 (N = 35), in 20 patients with tumor of stage T2c or greater. We therefore estimate that ultimately 25% of these patients failed. We assume that the ADC changes in patients who fail and patients who do not fail are both normally distributed, with the same SD but different means. We estimate this SD from the Barrett et al. data as $0.227/\sqrt{0.25^2+0.75^2} = 0.287$. In our study, with 30 patients, we expect approximately 8 treatment failures. Assuming 8 failures and a SD of 0.287, we will have 80% power to detect an absolute difference between the mean ADC change among those who fail treatment and those who do not of 0.51 SDs, or $0.51 \times 0.287 = 0.15 \times 10^{-3}$ mm²/s change in ADC. Barrett observed a baseline ADC mean in tumor of 1.006, hence we expect to be able to detect a change from baseline and 3-months ADT in ADC of approximately +/- 15% or greater.

5. Descriptive statistics will be used to enumerate the rectal V70's achieved using MRI versus CT data.

VIII Risks and Discomforts

Participants in this study will undergo a total of 3 follow up prostate MRIs. (Baseline standard of care prostate MRI prior to initiating therapy will be ordered by the treating physician). All MRIs will use a standard routine prostate MRI protocol without the use of an endorectal coil. Patients will receive Magnavist 0.1mmol/kg intravenously for each study, so renal function will need to be checked prior to

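### Section VII.4 claims 80% power to detect 0.51 SD between treatment failures and non-failures; with 8 versus 22 patients that difference has about 22% power, and 80% power needs about 1.20 SD.

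*Combined protocol and SAP*

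**What the plan says.** Section VII.4 sets up a comparison of two groups of patients. ADC changes in failures and non-failures are taken to be "both normally distributed, with the same SD but different means". The failure rate comes from this assumption: "We estimate that 25% of men with grade T2c or greater cancer will have end PSA greater than 0.5, and will fail therapy". For this study, "with 30 patients, we expect approximately 8 treatment failures", which leaves 22 non-failures.

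The power claim opens: "Assuming 8 failures and a SD of 0.287, we will have 80% power to detect an absolute difference between the mean ADC change among those". The rest of that sentence names the two outcome groups and sets the difference at 0.51 SD. Multiplied by the SD of 0.287, this becomes 0.15 × 10⁻³ mm²/s. Set against a baseline tumor ADC of 1.006, it is then presented as a detectable change in "ADC of approximately +/- 15% or greater".

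VII.4 names neither the test nor the significance level. VII.2 uses a two-tailed 0.05 paired t-test and VII.3 a two-tailed two-sample t-test, both adjusted for multiple time points.

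Section III includes a responder versus non-responder comparison in both endpoints. The secondary endpoint uses end PSA above 0.5 ng/ml, which is the definition behind VII.4. The primary endpoint uses a different failure definition, "defined as PSA end ADT values $>.3$ ng/ml".

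**The concern.** A detectable difference of about half an SD is implausibly small for 30 patients divided 8 to 22. The precision of a two-group comparison is governed by the smaller group, here 8 patients.

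VII.4 is the only power statement for any responder versus non-responder comparison, and such comparisons stand in both the primary and the secondary endpoint. A reader who trusts it would take a non-significant result as reasonable evidence against a 15% ADC difference, when the study would usually miss a difference of that size.

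**Working it through.** **Inputs (VII.4 unless noted)**
- N = 30; 8 failures, so 22 non-failures (0.25 × 30 = 7.5, rounded up)
- Common SD 0.287; baseline tumor ADC 1.006; power 80%
- Two-sided alpha 0.05: an assumption carried over from VII.2
- Two-sample t-test: an assumption that follows from the two independent groups and matches VII.3

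**1. The plan's surrounding arithmetic reproduces**
- 0.227 / √(0.25² + 0.75²) = 0.287
- 0.51 × 0.287 = 0.146, stated as 0.15
- 0.15 / 1.006 = 14.9%, stated as 15%

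These steps follow from the multiplier 0.51, so the question is where that comes from.

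**2. What reproduces 0.51**
- One-sample normal formula on all 30 patients: (1.960 + 0.842) / √30 = 0.5115
- The one-sample t-test with n = 30 gives 0.529

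The match to the one-sample formula is numerical. The plan does not state its formula.

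**3. The two-group calculation**
- Normal approximation: 2.802 × √(1/8 + 1/22) = 2.802 × 0.4129 = 1.157 SD
- Noncentral t, 28 df, noncentrality d × √(8 × 22/30) = 2.422 d: 80% power at d = 1.198 SD
- Power at d = 0.51 (noncentrality 1.235): 22.2%; by normal approximation 23.4%; in 100,000 simulated trials 22.1%
- At the rounded difference, 0.15 / 0.287 = 0.523 SD: 23.1%

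**4. In the plan's units**
- 1.198 × 0.287 = 0.344 × 10⁻³ mm²/s
- 0.344 / 1.006 = 34% of baseline

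**5. Sensitivity to what VII.4 leaves open**

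| Variant | SDs needed for 80% power | Power at 0.51 SD |
|---|---|---|
| 8 v 22, two-sided 0.05 | 1.20 | 22% |
| 8 v 22, one-sided 0.05 | 1.05 | 33% |
| 8 v 22, one-sided 0.10 | 0.89 | 47% |
| 8 v 22, two-sided 0.05/6 (factor from VII.2) | 1.53 | 7% |
| 7 v 23, two-sided 0.05 | 1.25 | 21% |
| 5 v 25, two-sided 0.05 | 1.42 | 17% |
| 15 v 15, two-sided 0.05 (best split) | 1.06 | 27% |

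The 5 v 25 row is illustrative. The 25% rate is stated for T2c or greater, while Section IV also admits T2b disease, or Gleason 7 or PSA ≥ 10 alone, so fewer failures are plausible.

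**6. Sensitivity to the SD**

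Dividing by √(0.25² + 0.75²) is not the variance relation for a mixture of two groups. If 0.227 is the overall SD across both groups, then 0.227² = s² + 0.25 × 0.75 × Δ², so the within-group SD s cannot exceed 0.227.
- With s = 0.227: detectable difference 1.198 × 0.227 = 0.27 (27%); power at 0.15 is 34%
- With s consistent with the mixture at the detectable difference: s = 0.227 / √(1 + 0.1875 × 1.198²) = 0.2015, so Δ = 1.198 × 0.2015 = 0.24 (24%)
- With s consistent with the mixture at Δ = 0.15: s = √(0.227² − 0.1875 × 0.15²) = 0.2175; power at 0.15 is 36%

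**7. Size needed for the claim as written**

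At the 8/30 failure share, 80% power at 0.51 SD needs about 156 patients, 42 of them failures.

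**8. The neighbouring sections**

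With SD 0.20 and a factor-6 correction, VII.2 gives 0.135 (stated 0.14). VII.3, taken as 30 v 30, gives 0.185 (stated 0.19). Both reproduce by t-test, so this multiplier error is confined to VII.4.

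**The case against.** The case for the plan has four parts.

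- **The test and alpha are not stated, so the one-sample origin is inferred.** This is correct, and both should be labelled as assumption and inference. The error does not depend on them: one-sided testing at 0.05 or 0.10 and every split of 30 patients fail. The 25/75 split is used in the SD step; it is absent only from the multiplier.
- **The SD of 0.287 is itself too large, so 22% overstates the problem.** In part this stands. At a difference of 0.15, power is 23% with the plan's SD and 34–36% with the smaller ones. The chance of missing it is then nearer two in three than four in five. None of these values approaches 80%.
- **Lesions rather than patients might be the unit.** VII.4 quotes N = 35 alongside 20 patients. If that means lesions, and the same rate applied here (35/20 × 30 ≈ 52, about 13 v 39, treated as independent), 80% power would still need about 0.91 SD.
- **The study is exploratory, and the correlation part of the primary endpoint has its own power statement in VII.1.** This is true and limits the consequence to interpreting the group comparison. No text says a null result would exclude a 15% difference. It does not make an incorrect power figure acceptable.

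**Conclusion.** The concern holds. For the comparison VII.4 describes, 80% power requires about 1.20 SD, not 0.51 SD, and power at 0.51 SD is about 22%. With the plan's SD of 0.287, the detectable difference is 0.34 × 10⁻³ mm²/s (34% of baseline), more than twice the stated 0.15 (15%). With an SD no larger than the reported 0.227, it is 0.24–0.27 (24–27%).

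These figures assume a two-sided 0.05 two-sample t-test without multiplicity adjustment and exactly 8 failures among 30 evaluable patients. Adjustment or fewer failures would make them worse.

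A related gap is that the primary endpoint's comparison at the 0.3 ng/ml cut-off has no power figure, because VII.4 uses the 0.5 ng/ml definition and a 3-month ADT change.

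**What to change.** Rewrite the power paragraph in VII.4:

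- State that with 8 failures and 22 non-failures, a two-sample t-test at two-sided 0.05 has 80% power to detect 1.20 SD.
- Give the absolute value with its SD named: 0.34 × 10⁻³ mm²/s (34% of 1.006) at SD 0.287. If the SD is re-derived from the mixture relation, give 0.24 (24%) instead; 0.27 (27%) applies if 0.227 itself is kept.
- Delete the 0.51 SD, 0.15 and 15% figures.
- Say that the comparison will be reported as an estimated difference with a 95% confidence interval. This goes beyond correcting the number, but it suits a comparison with this little power.
- For the 0.3 ng/ml comparison in the primary endpoint, state the expected failure rate and the matching detectable difference. The documents give no such rate; without one, only the lower bound of 1.06 SD (15 v 15) can be stated.

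The cost is the wording of one paragraph and a less favourable stated sensitivity. Sample size and procedures do not change.

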SCENARIO 2: He was seen by you in clinic on x/X/X. Do you think he is an acceptable research candidate for this study, and do I have your permission to contact him to discuss the study with him and determine his interest in participating, and if possible to obtain his consent?

For your convenience, the aim of the study, eligibility criteria, and what the study involves for your patient are as follows:

Aim of Study: To determine if there are measurable changes in prostate MRI that will help predict those who will or will not respond to ADT/EBRT

Eligibility Criteria:

1. Unfavorable intermediate- to high-risk localized disease:
 - Clinical or radiographic T2b-T4 primary tumor or
 - Gleason score 7-10 in any core or
 - PSA \geq 10 prior to initiation of therapy
2. Patients deemed suitable for therapy with ADT and EBRT and able to provide informed consent

What This Study Involves:

After confirming eligibility and obtaining consent:

Baseline non-coil prostate MRI prior to the start of ADT/EBRT

3 additional non-coil prostate MRIs over the next six months

PSA testing

The patient will not be charged for the additional MRIs, PSA levels, or for parking.

Sincerely,
[name]
